Appendix 6 cGVHD Response Assessment

Response Determination for Chronic GVHD Clinical Trials based on Clinician Assessments

Organ	Complete Response	Partial Response	Progression
Skin	NIH Skin Score 0 after	Decrease in NIH Skin Score	Increase in NIH Skin Score by
	previous involvement	by 1 or more points	1 or more points, except 0 to 1
Eyes	NIH Eye Score 0 after	Decrease in NIH Eye Score	Increase in NIH Eye Score by
	previous involvement	by 1 or more points	1 or more points, except 0 to 1
Mouth	NIH Modified OMRS 0 after previous involvement	Decrease in NIH Modified OMRS of 2 or more points	Increase in NIH Modified OMRS of 2 or more points
Esophagus	NIH Esophagus Score 0 after previous involvement	Decrease in NIH Esophagus Score by 1 or more points	Increase in NIH Esophagus Score by 1 or more points, except 0 to 1
Upper GI	NIH Upper GI Score 0 after previous involvement	Decrease in NIH Upper GI Score by 1 or more points	Increase in NIH Upper GI Score by 1 or more points, except 0 to 1
Lower GI	NIH Lower GI Score 0 after previous involvement	Decrease in NIH Lower GI Score by 1 or more points	Increase in NIH Lower GI Score by 1 or more points, except from 0 to 1
Liver	Normal ALT, alkaline phosphatase, and Total bilirubin after previous elevation of 1 or more	Decrease by 50%	Increase by 2 ≭ ULN
Lungs	 Normal %FEV1 after previous involvement If PFTs not available, NIH Lung Symptom Score 0 after previous involvement 	 Increase by 10% predicted absolute value of %FEV1 If PFTs not available, decrease in NIH Lung Symptom Score by 1 or more points 	 Decrease by 10% predicted absolute value of %FEV1 If PFTs not available, increase in NIH Lung Symptom Score by 1 or more points, except 0 to 1
Joints and fascia	Both NIH Joint and Fascia Score 0 and P-ROM score 25 after previous involvement by at least 1 measure	Decrease in NIH Joint and Fascia Score by 1 or more points or increase in P- ROM score by 1 point for any site	Increase in NIH Joint and Fascia Score by 1 or more points or decrease in P-ROM score by 1 point for any site
Global	Clinician overall severity score 0	Clinician overall severity score decreases by 2 or more points on a 0-10 scale	Clinician overall severity score increases by 2 or more points on a 0-10 scale

Abstracted from: Lee SJ, Wolff D, Kitko C, et al. Biol Blood Marrow Transplant 2015; 21:984 –999.

Appendix 7 cGVHD Lee Symptom Scale Score

By circling one number per line, please indicate how much you have been bothered by the following problems in the past 7 days:

Skin		Not at all	Slightly	Moderately	Quite a bit	Extremely
1.	Abnormal skin color	0	1	2	3	4
2.	Rashes	0	1	2	3	4
3.	Thickened skin	0	1	2	3	4
4.	Skin ulcer	0	1	2	3	4
5.	Itchy skin	0	1	2	3	4
Eyes and Mouth		Not at all	Slightly	Moderately	Quite a bit	Extremely
6.	Dry eyes	0	1	2	3	4
7.	Need to use eye drops frequently	0	1	2	3	4
8.	Difficulty seeing clearly	0	1	2	3	4
9.	Need to avoid certain foods due to mouth pain	0	1	2	3	4
10.	Ulcers in mouth	0	1	2	3	4
11.	Receiving nutrition from and intravenous line or feeding tube	0	1	2	3	4
Breathing		Not at all	Slightly	Moderately	Quite a bit	Extremely
12.	Frequent cough	0	1	2	3	4
13.	Colored sputum	0	1	2	3	4
14.	Shortness of breath with exercise	0	1	2	3	4
15.	Shortness of breath at rest	0	1	2	3	4
16.	Need to use oxygen	0	1	2	3	4
Eating and Digestion		Not at all	Slightly	Moderately	Quite a bit	Extremely
17.	Difficulty swallowing solid foods	0	1	2	3	4

Bittoi			Connacina			D1(101 201
18.	Difficulty swallowing liquids	0	1	2	3	4
19.	Vomiting	0	1	2	3	4
20.	Weight loss	0	1	2	3	4
Muscles and Joints		Not at all	Slightly	Moderately	Quite a bit	Extremely
21.	Joint and muscle aches	0	1	2	3	4
22.	Limited joint movement	0	1	2	3	4
23.	Muscle cramps	0	1	2	3	4
24.	Weak muscled	0	1	2	3	4
Energy		Not at all	Slightly	Moderately	Quite a bit	Extremely
25.	Loss of energy	0	1	2	3	4
26.	Need to sleep more/take naps	0	1	2	3	4
27.	Fevers	0	1	2	3	4
Mental Emotional		Not at all	Slightly	Moderately	Quite a bit	Extremely
28.	Depression	0	1	2	3	4
29.	Anxiety	0	1	2	3	4
30.	Difficulty sleeping	0	1	2	3	4

Appendix 8 PROMIS Global Health Score

Please answer each of the following questions and mark the box by selecting an appropriate answer for each question.

		Excellent	Very good	Good	Fair	Poor
01	In general, would you say your health is:	□ 5	4	3	2	1
02	In general, would you say your quality of life is:	5	□ 4	3	2	1
03	In general, how would you rate your physical health?	5	4	3	2	1
04	In general, how would you rate your mental health, including your mood and your ability to think?	□ 5	□ 4	3	□ 2	1
05	In general, how would you rate your satisfaction with your social activities and relationships?	5	4	3	2	1
09	In general, please rate how well you carry out your usual social activities and roles. (This includes activities at home, at work and in your community, and responsibilities as a parent, child, spouse, employee, friend, etc.)	5	□ 4	3	2	1
		Completely	Mostly	Moderately	A little	Not At
06	To what extent are you able to carry out your everyday physical activities such as walking, climbing stairs, carrying groceries, or moving a chair?	Completely 5	Mostly	Moderately	A little	Not At All
06	out your everyday physical activities such as walking, climbing stairs, carrying groceries, or moving a chair?	5	4	3	2	All 1
06	out your everyday physical activities such as walking, climbing stairs, carrying groceries, or moving a					All
	out your everyday physical activities such as walking, climbing stairs, carrying groceries, or moving a chair? In the past 7 days How often have you been bothered by emotional problems such as feeling anxious, depressed, or	5 Never	4 Rarely	Sometimes	Often	All 1 Always 1 Very
	out your everyday physical activities such as walking, climbing stairs, carrying groceries, or moving a chair? In the past 7 days How often have you been bothered by emotional problems such as feeling anxious, depressed, or	Never	Rarely	Sometimes 3	Often	All 1 Always
10	out your everyday physical activities such as walking, climbing stairs, carrying groceries, or moving a chair? In the past 7 days How often have you been bothered by emotional problems such as feeling anxious, depressed, or irritable? How would you rate your fatigue on	Never None		Sometimes	Often Severe	All 1

Appendix 9 cGVHD Activity Assessment-Patient Self Report

Symptoms												
Please rate how severe the following symptoms have been in the last 7days. Please fill in the circle below from 0 (symptoms has not been present) to 10 (the symptom was as bad as you can imagine it could be) for each item.		Not Present										As Bad As n Imagine
		0	1	2	3	4	5	6	7	8	9	10
Your skin itching at	its WORST?	0	0	0	0	0	0	0	0	0	0	0
Your skin and/or joi	Your skin and/or joint tightening at their WORST?		0	0	0	0	0	0	0	0	0	0
Your mouth sensitiv	ity at its WORST?	0	0	0	0	0	0	0	0	0	0	0
Your genital discom	fort at its WORST?											
(Women-vagina, vulv	va, or labia)	0	0	0	0	0	0	0	0	0	0	0
(Men-penis)												
Eyes	What is your main complaint v	vith regard	d to your	eyes?	•	•	•	•	•	•	•	•
	Please rate how severe this syn 0 (not at all severe) to 10 (mos		from	0	1 2	2 3	4	5	6	7	8 9	10

Patient Global Ratings:

1. Overall, do you think that your chronic graft versus host disease is mild, moderate or severe?

1=mild

2=moderate

3=severe

		r indicating how evere chronic (•	U	versus host dis	ease symptom	s are, where 0	is cGVHD syn	iptoms that ai	e not at all
0	1	2	3	4	5	6	7	8	9	10
cGVHD sym	•									evere cGVHD otoms possible
3. Compared +3 = Very mu		go, overall wou	ıld you say tha	ıt your cGVHI) symptoms ar	re:				
+2 = Modera										
+1 = A little b	oetter									
0 = About the	e same									
-1 = A little w	vorse									

Abstracted from: Lee SJ, Wolff D, Kitko C, et al. Measuring Therapeutic Response in Chronic Graft-versus-Host Disease. National Institutes of Health Consensus Development Project on Criteria for Clinical Trials in Chronic Graftversus-Host Disease: IV. The 2014 Response Criteria Working Group Report. Biol Blood Marrow Transplant 2015;21:984 – 999.

-2 = Moderately worse -3 = Very much worse

Appendix 10 Eastern Cooperative Oncology Group (ECOG) Performance Status

Score	Description
0	Fully active, able to carry on all pre-disease activities without restriction.
1	Restricted in physically strenuous activity but ambulatory and able to carry out work of a light or sedentary nature. For example, light housework, office work.
2	Symptomatic, <50% in bed during the day (Ambulatory and capable of all self care but unable to carry out any work activities. Up and about more than 50% of waking hours).
3	Symptomatic, >50% in bed, but not bedbound (Capable of only limited self-care, confined to bed or chair 50% or more of waking hours).
4	Bedbound (Completely disabled. Cannot carry on any self-care. Totally confined to bed or chair).
5	Death.

Appendix 11 Calculation Formula of Creatinine Clearance

Male:

 $Ccr=[(140-Age)\times Weight(kg)]/[0.818\times Scr (\mu mol/L)]$

Female:

 $Ccr=[(140-Age)\times Weight(kg)]/[0.818\times Scr (\mu mol/L)]\times 0.85$

Annotation:

Ccr= Creatinine Clearance; Scr = Serum Creatinine

 $Scr (mg/dL) = Scr (\mu mol/L) \times 0.01131$

Appendix 12 Drugs that Induce and Inhibit CYP3A4

	Strong	Moderate	Weak
Inducers	Apalutamide Carbamazepine Enzalutamide Mitotane Phenytoin Rifampin	Bosentan Efavirenz Etravirine Phenobarbital Primidone	Armodafinil Modafinil Rufinamide
Inhibitiors	St. John's wort Boceprevir Cobicistat Conivaptan Danoprevir Dasabuvir Elvitegravir Grapefruit juice Indinavir Itraconazole Ketoconazole Lopinavir Paritaprevir Ombitasvir Posaconazole Ritonavir Saquinavir Telaprevir Tipranavir Telithromycin Troleandomycin Voriconazole	Aprepitant Ciprofloxacin Kaunivartan Crizotinib Cyclosporine Diltiazem Dronedarone Erythromycin Fluconazole Fluvoxamine Imatinib Tofisopam Verapamil	Chlorzoxazone Cilostazol Cimetidine Clotrimazole Fosaprepitant Istradefylline Ivacaftor Lomitapide Ranitidine Ranolazine Ticagrelor

This is not a comprehensive list, and all concomitant medications should be evaluated for possible interactions with BN101/belumosudil.

Data Source:

 $\underline{https://www.fda.gov/drugs/developmentapprovalprocess/developmentresources/druginteractionslabeling/ucm093664.htm}$

Appendix 13 Drugs that Induce and Inhibit CYP1A2

	Strong	Moderate	Weak
Inducers	-	Phenytoin Rifampin Ritonavir Smoking Teriflunomide	-
Inhibitors	Ciprofloxacin Enoxacin Fluvoxamine	Methoxsalen Mexiletine Oral contraceptives	Acyclovir Allopurinol Cimetidine Peginterferon α-2a Piperine Zileuton

This is not a comprehensive list, and all concomitant medications should be evaluated for possible interactions with BN101/belumosudil.

Data Source:

https://www.fda.gov/drugs/developmentapproval process/development resources/drug interactions labeling/ucm 093664. htm

Protocol Version 3.0 Version Date: 25 Feb 2022

Appendix 9 Drugs that Prolong QT/QTc

Gener	ic Name
Aclarubicin	Hydroxychloroquine
Amiodarone	Ibogaine
Anagrelide	Ibutilid
Arsenic trioxide	Levofloxacin
Astemizole	Levomepromazine
Azithromycin	Levomethadyl acetate
Bepridil	Levosulpiride
Chloroquine	Mesoridazine
Chlorpromazine	Methadone
Chlorprothixene	Moxifloxacin
Cilostazol	Nifekalant
Ciprofloxacin	Ondansetron
Cisapride	Oxaliplatin
Citalopram	Papaverine HCl
Clarithromycin	Pentamidine
Cocaine	Pimozide
Disopyramide	Probucol
Dofetilide	Procainamide
Domperidone	Propofol
Donepezil	Quinidine
Dronedarone	Roxithromycin
Droperidol	Sevoflurane
Erythromycin	Sotalol
Escitalopram	Sparfloxacin
Flecainide	Sulpiride
Fluconazole	Sultopride
Gatifloxacin	Terfenadine
Grepafloxacin	Terlipressin
Halofantrine	Terodiline
Haloperido	Thioridazine
Dihydroquinidine	Vandetanib

This is not a comprehensive list, and all concomitant medications should be evaluated for possible interactions with BN101/belumosudil.

Data Source: https://www.crediblemeds.org/pdftemp/pdf/CombinedList.pdf (30 Dec 2019)

Appendix 10 Equivalent Dose of Corticosteroid Hormone

Class of Drug	Name of Drug	Equivalent Dose (mg)
Short-acting	Hydrocortisone	20
	Cortisone	25
Medium-acting	Prednisone	5
	Prednisolone	5
	Methylprednisone	4
Long-acting	Triamcinolone acetonide	4
	Betamethasone	0.60
	Dexamethasone	0.75
Hydrocortisone 1 = Cor	tisone 0.8 = Prednisone 4 = Pre	ednisolone 4 = Methylprednisone 5 = Triamcinolone

Hydrocortisone 1 = Cortisone 0.8 = Prednisone 4 = Prednisolone 4 = Methylprednisone 5 = Triamcinolone acetonide 5 = Betamethasone 25 = Dexamethasone 20

Annotation -

The ratio of anti-inflammatory effect is based on counting hydrocortisone as 1. The equivalent dose is counted with a standard of hydrocortisone.

Data Source: http://news.medlive.cn/imm/info-progress/show-150532 166.html

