7.1.2 Secondary efficacy endpoints/indicators

Secondary efficacy endpoints included median Duration of Response (DOR), Change in Lee

Symptom Scale Score, Response rate by organ system, Percentage of subjects with best efficacy as PR and percentage of subjects with best efficacy as CR, Change in corticosteroid dose, Change in CNI dose, Failure-Free Survival (FFS), Overall Survival (OS), Change in cGVHD severity based on the Physician-Reported Global cGVHD Activity Assessment, and Change in symptom activity based on cGVHD Activity Assessment Patient Self-Report.

Lee Symptom Scale Score

Changes in symptom burden/bother will be explored using the Lee cGVHD Symptom Scale (Appendix 7). Symptom burden will be assessed on Screening/Day 1 of each cycle starting on Cycle 1 Day 1, as well as at the EOT visit. The questionnaire asks subjects to indicate the degree of bother that they experienced due to symptoms in seven domains potentially affected by chronic GVHD (skin, eyes, mouth, breathing, eating and digestion, energy, and emotional distress). The degree to which subjects report that they are bothered by a symptom represents a global assessment incorporating not only the intensity of the symptom and its frequency, but also the degree to which it causes emotional disturbance or interferes with functioning.

cGVHD Activity Assessment – Patient Self Report (Appendix 9)

Changes in the cGVHD Activity Assessment – Patient Self Report will be evaluated.

Change in Corticosteroid Dose

The change in systemic corticosteroid dose over time will be determined. If subjects are not using prednisone as the corticosteroid therapy, then the prednisone dose equivalent will be determined. See Appendix 15 for specific corticosteroid equivalent dose conversions.

Failure Free Survival (FFS)

FFS is defined as the absence of cGVHD treatment change, non-relapse mortality and recurrent malignancy.

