Response assessment by physician for the nine individual organs (skin, eyes, mouth, esophagus, upper GI, lower GI, liver, lungs and joints and fascia) plus global severity rating will be collected in eCRF.

Time to Response (TTR)

TTR is defined as the time from first treatment to the time of first documentation of response.

Time to Next Therapy (TTNT)

TTNT is defined as the time from first treatment to the time of new systemic cGVHD treatment, censored by last response assessment or long term follow up assessment, which ever is the latest and available.

Corticosteroid Dose

Corticosteroid doses will be presented as mg/kg/day prednisone equivalent dose. If a patient is not using prednisone as the systemic corticosteroid, then the prednisone dose equivalent will be determined according to following conversion ratios:

1mg prednisone is equivalent to:

- 4mg Hydrocortisone
- 0.8mg Methylprednisolone
- 0.15mg Dexamethasone

- 1mg Prednisolone
- 0.8mg Triamcinolone

Transient increase in corticosteroid dosing (not exceeding 1mg/kg/day prednisone equivalent) is permitted for the treatment of cGVHD flare, but dose must be reduced back to the pre-enrollment dose within 6 weeks. If the dose remains elevated for more than 6 weeks, this will be considered a BN101/belumosudil treatment failure. More than 2 episodes of cGVHD flare requiring increased corticosteroid in the first month of BN101/belumosudil treatment will also be considered a BN101/belumosudil treatment failure.

Calcineurin Inhibitor (CNI) Dose

CNI includes systemic tacrolimus and cyclosporine.

Failure Free Survival (FFS)

FFS is defined as the absence of new cGVHD systemic therapy, non-relapse mortality and recurrent malignancy (e.g. underlying disease) and is censored by last response assessment or long term follow up assessment, whichever is the latest and available.

Overall Survival (OS)

OS is defined as time from first dose of BN101/belumosudil to the date of death due to any cause.

Change in cGVHD severity using the Clinician-Reported Global cGVHD Activity Assessment

The Clinician-reported global cGVHD Activity Assessment is a 0-10 point numeric rating scale with a score 0 indicating “cGVHD symptoms not at all severe” and a score of 10 being “most severe cGVHD symptoms possible”. The activities are assessed on Day 1 of each cycle from Cycle 1 Day 1 to EOT.

Change in symptom activity using the cGVHD Activity Assessment Patient Self-Report

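### The corticosteroid appendix's dose column and its potency line differ by a factor of 1.33 for dexamethasone and betamethasone, and the SAP gives no betamethasone factor

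*Protocol*

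**What the plan says.** Protocol 7.1.2 makes change in systemic corticosteroid dose a secondary endpoint, expressed as prednisone equivalent, and directs the reader to the appendix: "See Appendix 15 for specific corticosteroid equivalent dose conversions". The contents list also numbers that appendix 15, but its page heading prints 10.

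The appendix holds two sets of figures. The first is a column of equivalent doses in mg, including "Hydrocortisone 20", "Betamethasone 0.60" and "Dexamethasone 0.75", with prednisone at 5. The second is a line of ratios that starts from hydrocortisone at 1, puts prednisone at 4 and ends "Betamethasone 25 = Dexamethasone 20". The annotation explains the line: "The ratio of anti-inflammatory effect is based on counting hydrocortisone as 1". It says that the dose column uses hydrocortisone as its standard too.

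The protocol sets three limits in prednisone equivalents. Inclusion criterion 4 (section 3.1) uses more than 0.5 mg/kg/day in its second route and more than 0.25 mg/kg/day in its third. Section 6.4.1 caps a transient increase during a cGVHD episode at 1 mg/kg/day.

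SAP 5.1.2 carries its own short conversion list per 1 mg of prednisone. It includes "0.15mg Dexamethasone" but neither betamethasone nor cortisone, both of which the appendix lists.

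**The concern.** A potency relative to hydrocortisone and an equivalent dose relative to hydrocortisone are the same information written two ways; one is the inverse of the other. If they disagree for a drug, the appendix gives two answers for that drug, and nothing in the protocol says which one governs.

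What could be affected is the classification of a dose against the three mg/kg/day limits at site level, and the mg/kg/day values in the steroid-dose endpoint. For betamethasone the second matters more. The SAP has no factor for it, so an analyst would have to turn to the protocol appendix, the only other conversion source in the two documents.

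**Working it through.** **Inputs.** Equivalent doses and printed ratios come from the protocol appendix, the limits from criterion 4 and section 6.4.1, and the SAP factor from SAP 5.1.2. Body weight is not in the documents; 60 kg is assumed, with 50 and 70 kg as a range.

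**Step 1: consistency of the appendix.** Implied ratio = hydrocortisone dose / drug dose = 20 / dose.

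| Drug | Dose column (mg) | 20 / dose | Printed ratio |
|---|---|---|---|
| Hydrocortisone | 20 | 1 | 1 |
| Cortisone | 25 | 0.8 | 0.8 |
| Prednisone | 5 | 4 | 4 |
| Prednisolone | 5 | 4 | 4 |
| Methylprednisone | 4 | 5 | 5 |
| Triamcinolone acetonide | 4 | 5 | 5 |
| Betamethasone | 0.60 | 33.3 | 25 |
| Dexamethasone | 0.75 | 26.7 | 20 |

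The formula reproduces six printed ratios exactly, so the two sets are meant to be inverses. The other two miss by the same factor: 26.67/20 = 33.33/25 = 1.333.

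**Step 2: prednisone equivalent per mg of drug.** Column: 5 / dose. Ratio line: ratio / 4.

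- Dexamethasone: 5/0.75 = 6.67 mg by the column; 20/4 = 5.00 mg by the ratio line.
- Betamethasone: 5/0.60 = 8.33 mg by the column; 25/4 = 6.25 mg by the ratio line.
- SAP, dexamethasone: 1/0.15 = 6.67 mg, the same as the column (0.75/5 = 0.15).

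**Step 3: against the limits at an assumed 60 kg.** Value = daily dose × factor / 60.

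| Drug and dose | Column | Ratio line | Limit (mg/kg/day) |
|---|---|---|---|
| Dexamethasone 2.5 mg/day | 0.28 | 0.21 | > 0.25 (criterion 4) |
| Dexamethasone 5 mg/day | 0.56 | 0.42 | > 0.5 (criterion 4) |
| Betamethasone 4 mg/day | 0.56 | 0.42 | > 0.5 (criterion 4) |
| Dexamethasone 10 mg/day | 1.11 | 0.83 | maximum 1 (6.4.1) |

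In each row the two readings fall on opposite sides of the limit.

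**Step 4: the range of doses affected.** Each edge of the discordant band is limit × weight / factor. For dexamethasone at 60 kg and the 0.5 limit, the edges are 30/6.67 = 4.5 and 30/5 = 6.0 mg/day. Doses above the lower edge, up to and including the upper edge, are classified differently.

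| Limit (mg/kg/day) | Dexamethasone, 60 kg (mg/day) | Betamethasone, 60 kg (mg/day) |
|---|---|---|
| 0.25 | 2.25 to 3.0 | 1.8 to 2.4 |
| 0.5 | 4.5 to 6.0 | 3.6 to 4.8 |
| 1 | 9.0 to 12.0 | 7.2 to 9.6 |

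At the 0.5 limit the dexamethasone band is 3.75 to 5.0 mg/day at 50 kg and 5.25 to 7.0 mg/day at 70 kg. The upper edge is always 1.333 times the lower, so a band exists at any weight. The lower edge itself is not discordant: dexamethasone 9 mg/day at 60 kg is exactly 1.00 by the column and 0.75 by the ratio line, and both comply with the cap.

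**The case against.** The mismatch cannot be disputed: the figures are legible and six other drugs pass the same check. The case on the other side concerns consequences, and much of it stands.

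- *The ratio line is not presented as a dose converter.* The appendix title and the column heading both speak of equivalent dose, as does the cross-reference in 7.1.2; the line beneath is described as anti-inflammatory effect. Most sites would use the column. A reader might infer that sites and the SAP will disagree; the documents support only that they could.
- *The treatment-failure rules do not turn on a mg/kg threshold.* Section 6.4.1 defines failure by a dose still elevated after six weeks, or by too many episodes needing an increase. Going above 1 mg/kg/day is not listed as failure. For a patient who stays on one drug the factor cancels in the comparison with the pre-enrolment dose, so the six-week rule is affected only if the drug changes.
- *Eligibility need not change.* Criterion 4 offers three alternative routes. The first, a stable dose over the two weeks before screening, has no mg/kg limit, so missing 0.5 or 0.25 does not by itself exclude a patient.
- *Neither criterion 4 nor 6.4.1 cites the appendix.* Only 7.1.2 does. Applying it to the limits is an inference, though it is the only conversion the protocol offers.
- *The dexamethasone analysis has one answer.* The SAP fixes its factor. Percent change and the counts of patients reducing or stopping steroids do not depend on the factor for a patient on a single drug.

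What remains is the contradiction itself, its possible effect on site-level classification against the three limits, and the missing betamethasone factor in the SAP. Cortisone is only a gap in the SAP list, because its two appendix figures agree.

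**Conclusion.** The appendix contradicts itself by a factor of 1.33 for dexamethasone and betamethasone and for no other drug. That follows from its own figures and needs no assumption. The column's prednisone equivalent is one third above the ratio line's; read the other way, the ratio line is 25% below the column.

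The difference can move a dose across the 0.25, 0.5 and 1 mg/kg/day limits. The particular doses depend on the assumed weight; the existence of a discordant band does not. In the analysis, the unresolved quantity is the absolute mg/kg/day value for betamethasone.

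It would go too far to conclude that patients will be wrongly enrolled or excluded, that treatment failures will be misclassified, or that the steroid endpoint is undefined as a whole. The stable-dose route, the within-patient comparison in the six-week rule and the SAP's fixed dexamethasone factor each stand against one of those readings. The effect is confined to patients on systemic dexamethasone or betamethasone, and the documents do not say how many of the 30, if any, are expected. This is a minor item, worth correcting because the correction is nearly free.

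**What to change.** Reconcile the dose column and the ratio line to a single set of factors. State in the protocol that this set applies to inclusion criterion 4 and section 6.4.1 as well as to the dose endpoint, and use the same set in SAP 5.1.2. From it, add the betamethasone factor to the SAP list, and cortisone for completeness. Correct the appendix number at the same time, so that the cross-reference in 7.1.2 leads to the page. Which conversion is right is for the sponsor to settle; this review proposes neither.

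The cost is a correction to one line of the appendix, a sentence on where it applies, and two lines in the SAP. No data collection or design feature changes.
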